4. GENERAL ANALYTIC CONSIDERATIONS

4.1. Study Size and Power

A total of approximately 500 patients will be randomized using a 1:1 assignment ratio. The sample size is selected to achieve at least 80% power to detect a difference at the 0.05 level of significance (2-sided) in the proportion of patients who experience any emergency room visit or hospitalization, or death over 28 days.

This sample size is based on an assumed 3% event rate for the sargramostim arm and a 10% rate for the placebo arm (risk ratio of 0.30) in unvaccinated patients (similar to that observed for bamlanivimab BLAZE-1 study [Chen, 2021; Gottlieb, 2021; US FDA, 2021]). As discussed in protocol Section 4.6, the rate of any emergency room visits or hospitalization, or death over 28 days is expected to be very low, or near zero for vaccinated patients.

It is also assumed that the proportion of vaccinated patients will be approximately 20-25% of the study population, with enrollment of patients who have completed a COVID-19 vaccination regimen or participated in a COVID-19 vaccine clinical trial capped at approximately 100 patients; no events are expected to occur in these patients for either treatment arm. Therefore, the overall event rate (for unvaccinated and vaccinated patients combined) for the primary endpoint is expected to be 2.4% for sargramostim and 8.0% for placebo (risk ratio of 0.30) and maintains at least 80% power.

Note that completion of a COVID-19 vaccination regimen or participation in a COVID-19 vaccine clinical trial (yes, no) is one of the randomization stratification factors (protocol Section 6.2).

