The primary estimand of treatment effect will be the risk difference between treatment arms, corresponding 95% confidence interval (CI), and p-value based on a Wald test. The confidence interval for the risk difference will be obtained using the delta method. Additionally, the odds ratio, corresponding 95% CI, and p-value will be generated.

The proportion of patients who have any ER visit, hospitalization, or death by Days 7, 14 and 28, and at any time during the study (e.g., to Day 60) will be tabulated. A Chi-square or Fisher’s exact test will compare treatment arms at each timepoint of interest. Number and percentage of patients who experience each type of healthcare as listed on the Hospitalization eCRF will also be tabulated by treatment arm.

Individual data listings of ER visits, hospitalizations, or deaths will be provided with an indication of whether or not the event occurred by Day 28 and whether or not the event was COVID-19-related, along with treatment arm, randomization strata, age, race, and sex for each patient.

Two sensitivity analyses will be conducted mirroring primary endpoint analysis methods as specified above.

1. The first sensitivity analysis will define the endpoint as any COVID-19-related emergency room visits, COVID-19-related hospitalizations, or deaths (any cause).
2. The second sensitivity analysis will define the endpoint the same way as the primary analysis, but will be conducted using the mITT Population.

A third sensitivity analysis will be conducted if the primary endpoint is missing for 5% or more of patients; i.e., missing the primary endpoint, in this case, refers to patients who were not followed through Day 28, and were not known to have an ER visit, hospitalization, or death. This analysis will use a multiple imputation approach (such as Marcov Chain Monte Carlo method, or FCS method with logistic regression) to impute missing values for patients who are missing the primary endpoint due to loss to follow-up or discontinuation prior to Day 28 (Little 2019). Covariates to consider when imputing the missing data will at a minimum include treatment arm, and those listed in [Section 12.1](#).

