12. EXPLORATORY ANALYSES

12.1. Subgroup Analysis and Adjustment for Covariates

All subgroup analyses and covariate adjustments will be treated as exploratory since the study was not powered for such analyses. These analyses will be conducted using the FAS, unless otherwise specified. The following baseline characteristics will be considered for subgroup analyses and covariate adjustment in statistical models. Additional baseline factors may be considered for these analyses and a decision on which factors to include will be made while the study team remains blinded.

- Age group (18-59, \geq 60 years). For regulatory purposes, an additional analysis may be performed using age groups defined as 18-64, and \geq 65 years. If there are enough patients \geq 75 years or \geq 85 years, these categories may be included.
- Number of pre-existing medical conditions which put patients at higher risk of progression to severe COVID-19 (0-1, 2 or more), based on Inclusion Criterion 3b. Note: age will be considered separately as denoted above. If there are enough patients for any specific pre-existing condition in Inclusion Criterion 3b, a subgroup analysis may be performed for this.
- Duration of any COVID-19 symptoms (0-2, 3-5 days)
- Baseline NIAID ordinal score (1, 2)
- Gender (male, female)
- Race (White, Black or African American, Asian, all others)
- Ethnicity (Hispanic or Latino, Not Hispanic or Latino)
- Body mass index ($<18.5 \text{ kg/m}^2$, $18.5 \text{ to } <25 \text{ kg/m}^2$, $\geq 25 \text{ to } <30 \text{ kg/m}^2$, $\geq 30 \text{ kg/m}^2$)
- Baseline SARS-CoV-2 variant (groupings to be determined based on prevalence)
- Use of approved/authorized COVID-19 therapies prior to randomization (if there are sufficient number of patients)

In addition to the above baseline factors, the following 2 randomization stratification factors will be used for subgroup analyses and included in all covariate adjustment models if there are sufficient patients in each of the strata.

- Region (US, outside US)
- Completion of a COVID-19 vaccination regimen or participation in a COVID-19 vaccine clinical trial (yes, no).

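### If the third sensitivity analysis uses ordinary FCS logistic imputation, its covariate floor includes a vaccination stratum expected to have no events, so the model separates and imputes spurious events

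*SAP*

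**What the plan says.** **Primary rule and trigger.** SAP Section 9.1 counts a patient lost before Day 28 as having no event. A third sensitivity analysis relaxes that rule by multiple imputation, but only if the primary endpoint is missing for 5% or more of patients. MCMC and FCS with logistic regression are given as examples of the method.

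**Covariates.** "Covariates to consider when imputing the missing data will at a minimum include treatment arm, and those listed in" Section 12.1. That section introduces its list with "The following baseline characteristics will be considered for subgroup analyses and covariate adjustment in statistical models". It names ten baseline factors and adds region and vaccination. Prior COVID-19 therapy, region and vaccination depend on there being enough patients, and sparse categories may be combined on the same basis.

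**Expected events.** Section 4.1 takes an "assumed 3% event rate for the sargramostim arm and a 10% rate for the placebo arm (risk ratio of 0.30) in unvaccinated patients". Enrolment of vaccinated patients is "capped at approximately 100 patients", and of them the SAP says that "no events are expected to occur in these patients for either treatment arm".

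**Precautions elsewhere.** The primary model in Section 9.1 has treatment alone and a Firth penalty. Event rates within strata are to be looked at before any stratified analysis. Neither precaution is stated for the imputation model.

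**The concern.** A logistic model that contains an indicator for a group with no events has no finite maximum likelihood estimate for that coefficient. The fitted value drifts towards minus infinity with a huge standard error. FCS imputation draws coefficients from a distribution centred on the estimate with that spread. The draws therefore swing between event probabilities near 0 and near 1, and missing patients in the group are imputed as events about half the time although none are expected.

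The SAP predicts this situation for vaccinated patients. Section 4.1.1 also expects a very low or near-zero rate in patients given authorised therapies, so prior therapy on the Section 12.1 list could be a second sparse level.

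This is the only planned primary-endpoint analysis that drops the rule that a lost patient has no event. Power is only about 80% to begin with. A loss of significance caused by the imputation model could be read as fragility of the primary result under missing data.

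**Working it through.** **1. The plan's own figure.** Section 4.1 says that the overall rate "is expected to be 2.4% for sargramostim and 8.0% for placebo (risk ratio of 0.30) and maintains at least 80% power". With 250 per arm and a pooled rate of 0.052, power = Φ{[0.056 − 1.96·√(2 × 0.052 × 0.948/250)] / √[(0.08 × 0.92 + 0.024 × 0.976)/250]} = 80.7%. The figure is reproduced.

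**2. Expected events.** 250 × 0.024 + 250 × 0.080 = 6 + 20 = 26. With 5% missing, about 26 × 0.95 = 24.7 are observed. Expected vaccinated events: 0 of about 100 patients.

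**3. Slopes in the listed model** (levels minus one):

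| Factor | Slopes |
|---|---|
| Age, conditions, symptom duration, NIAID score, gender, ethnicity | 6 |
| Race (4 levels), BMI (4 levels) | 3 + 3 |
| Prior therapy, region, vaccination | 3 |
| Variant (grouping left open; 2 to 4 levels assumed) | 1 to 3 |
| Treatment | 1 |
| **Total** | **17 to 19** |

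That is 26/19 = 1.4 to 26/17 = 1.5 events per slope, before missingness indicators.

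**4. Simulation.** 400 trials of 500 patients, 20% vaccinated with no events, outcomes missing completely at random, 50 imputations. Covariate prevalences were assumed, and the other factors were given no effect on outcome. Where two sets of runs were made, both results are shown.

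| Imputation model | Imputed events, 5% missing (true about 1.3) | Of these, vaccinated (true 0) | Imputed events, 10% missing (true 2.5 to 2.75) |
|---|---|---|---|
| Full list, ordinary ML | 4.6 to 4.7 | 2.4 to 2.5 of about 5 | 9.7 to 9.8 |
| Treatment + vaccination, ordinary ML | 3.8 | 2.5 | 7.9 |
| Full list, data-augmented | 2.1 | 0.15 | 4.3 to 4.4 |
| Full list, Firth | 2.05 | 0.09 | 4.3 |
| Treatment only, ordinary ML | 1.3 | 0.27 | 2.7 to 2.9 |
| Normal-model MCMC, unrounded | 1.3 | 0.0 | 2.65 |

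The full ordinary model separated in every trial. With a 1% vaccinated event rate instead of zero, it still separated on some level in 84% to 87% of trials and imputed about 23% of missing vaccinated patients as events.

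**5. Effect on the risk difference.** Rubin's rules: SE² = p₀(1−p₀)/250 + p₁(1−p₁)/250 + (1 + 1/50)B², where B is the between-imputation SD.

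- 5% missing, full ordinary model: rates 0.0867 and 0.0307, B = 0.0066. SE = √(0.000436 + 0.000044) = 0.0219.
- 5% missing, treatment only: rates 0.0798 and 0.0241, B = 0.0045. SE = √(0.000388 + 0.000021) = 0.0202. Ratio 1.08.
- 10% missing, full ordinary model: rates 0.0944 and 0.0380, B = 0.0096. SE = √(0.000488 + 0.000094) = 0.0241.
- 10% missing, treatment only: rates 0.0800 and 0.0248, B = 0.0067. SE = √(0.000391 + 0.000046) = 0.0209. Ratio 1.15.

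At 5% missing the mean risk difference is 0.0560 under the full ordinary model against a true 0.0557, so bias is negligible.

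**6. Against the repaired model.** A further simulation compared the full ordinary model with a penalised or augmented model holding treatment, vaccination, age group and number of risk conditions. At 5% missing, the ordinary model imputed 4.6 events (1.4 true), with SE 0.0219 and power 75%. The repaired model imputed 1.5 events, with SE 0.0203 and power 80% to 81%. At 10% missing, power was 71% against 81% to 82%.

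**The case against.** A reader might infer that the SAP obliges the statistician to include every Section 12.1 factor, that too many parameters for 26 events must make the model separate, and that the result could overturn the primary finding. The documents do not support that.

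- **Inclusion.** The sentence mixes covariates to consider with a stated minimum, and some Section 12.1 factors are conditional. The stricter reading is natural but not the only one. The conditions count patients, however, and about 100 vaccinated patients would pass them.
- **Method.** MCMC and FCS are only examples. Normal-model MCMC does not separate, and the SAP does not say whether an FCS model would be penalised. This stands, so the harm is conditional on an ordinary FCS logistic fit.
- **Cause.** Treatment plus vaccination alone, fitted by ordinary ML, gives the same vaccinated excess. The empty stratum is the main driver. The long list adds a smaller excess that remains under Firth (2.05 against 1.3 events).
- **Consequence.** The risk difference hardly moves, because spurious events fall in both arms. The damage is noise and lost power, not a shifted estimate.
- **General provisions.** Section 4.5 allows further missing-data rules before unblinding, Section 5.3 leaves final imputation of endpoints to blinded review, and Section 4.6 allows alternative methods if assumptions fail. Pooled zero events in vaccinated patients would be visible without unblinding. These provisions could rescue the analysis, but they name no trigger or method and leave the stated covariate floor in place.
- **Precision.** With 400 trials, a simulated power near 80% has a Monte Carlo error of √(0.8 × 0.2/400) = 2 points. Under separation, the imputed rate also depends on the software. The power losses are approximate; the SE increase also follows from the arithmetic above.

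**Conclusion.** The point holds in conditional form. The SAP permits ordinary FCS logistic imputation with a covariate floor that contains a stratum it expects to have no events, and it states no rule for separation. Under that option, about three extra events are imputed at 5% missing and about seven at 10%. SE rises about 8% and 15%, and power falls about 5 to 6 and 10 points.

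These sizes rest on the SAP's event rates, a vaccinated share of 20% with no events, assumed covariate prevalences and 2 to 4 variant levels, and outcomes missing at random. The vaccinated excess roughly halves if the vaccinated event rate is 1%.

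The primary analysis is not affected, and nothing arises if fewer than 5% of endpoints are missing. The change is worth making because it is cheap and the failure can be foreseen from the SAP's own assumptions.

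**What to change.** **Essential.** In Section 9.1, state that any logistic imputation model will be fitted with a Firth-penalised or data-augmented likelihood. With the full list kept, this alone cuts imputed vaccinated events at 5% missing from about 2.5 to 0.15 or fewer.

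**Secondary.** Replace the minimum list taken from Section 12.1 with a short pre-specified set, for example treatment, vaccination stratum, age group and number of risk conditions. Alternatively, keep the list but allow factors to be collapsed or dropped by pooled blinded event counts, not patient counts.

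**Cost.** SAP wording and a programming option, settled before unblinding. A shorter list gives up auxiliary variables that might make the missing-at-random assumption more plausible; the penalised or augmented fit does not.

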9.2. Analysis of Secondary Outcome Measures

Secondary efficacy analyses will be performed using the FAS unless otherwise specified. Individual data listings of NIAID ordinal scale results, symptom score questions and overall symptom score will be provided for each available day of record along with treatment arm, randomization strata, age, race, and sex for each patient.

In the event of missing NIAID ordinal assessments, any available hospitalization records, supplemental oxygen use information, or death information, as well as patient reported outcomes, will be used to impute the NIAID ordinal score if possible, particularly for ordinal scores by Days 7, 14, 28 and 60. This imputation will be conducted in a blinded fashion by the medical monitor and results will be provided to the data management/statistical team. If there is a missing assessment that is unable to be imputed using the data described above, but the missing assessment occurs between two non-missing assessments, then the higher non-missing score will be imputed for the missing score. Imputed scores will be used in the analyses below (unless specified otherwise, i.e., for sensitivity analyses) and any missing scores that are unable to be imputed will be ignored. If less than 5% of expected NIAID ordinal assessments are missing and unable to be imputed, then any impact on analysis will be considered negligible and no further action will be taken. If 5% or more are missing and unable to be imputed, then the study team will consider imputing an appropriate “high score” that is reasonable based on other responses. This “high score” will be chosen and documented prior to unblinding.

9.2.1. Proportion of patients with any progression of disease as determined by a ≥ 2 -point increase in the NIAID ordinal scale up to Day 28 and Day 60

A secondary endpoint is the proportion of patients with progression of disease as determined by a ≥ 2 -point increase in the NIAID ordinal scale up to Days 28 and 60 (e.g., a change from 2 to 4, or a change from 2 to 5). The analysis will be performed for each timepoint using a logistic regression model with a Firth penalized likelihood (Firth, 1993) at the two-sided 0.05 significance level. The model will include treatment as the independent variable. Event rates within strata will be evaluated to determine whether it is appropriate to conduct a sensitivity analysis which includes stratification by the randomization stratification factors for geographic

region (US vs outside US) and completion of a COVID-19 vaccination regimen or participation in a COVID-19 vaccine clinical trial (yes, no).

The primary estimand of treatment effect will be the risk difference between treatment arms, corresponding 95% confidence interval (CI), and p-value based on a Wald test. The confidence interval for the risk difference will be obtained using the delta method. Additionally, the odds ratio, corresponding 95% CI, and p-value will be generated.

The proportion of patients with any progression of disease as defined above by Days 7, 14, 28 and 60 will be tabulated. A Chi-square or Fisher's exact test will compare treatment arms at each timepoint of interest.

A sensitivity analysis will be conducted mirroring analysis methods described above but excluding any imputed scores. A repeated measures modelling approach may also be considered to utilize the available longitudinal data.

9.2.2. Time to progression of disease as determined by a \geq 2-point increase in the NIAID ordinal scale up to Day 28 and Day 60

Time to progression of disease will also be assessed. Time to progression is defined as time from randomization to first occurrence of a \geq 2-point increase in the NIAID ordinal scale up to Day 60. Patients who do not have a \geq 2-point increase in the NIAID ordinal scale by Day 60 will be censored at the date of their last non-missing NIAID assessment up to Day 60. Kaplan-Meier methods will be used for the first time to event analysis. A log rank test stratified by the 2 randomization stratification factors, as appropriate, will be used to compare the 2 treatment arms. Estimates for probability of progression at Days 7, 14, 28, and 60 days, as well as median time to progression, will be derived from Kaplan Meier analysis.

Cox's proportional hazards model stratified by the 2 randomization stratification factors, as appropriate, will also be used to derive a hazard ratio and 95% CI assessing treatment effect, along with comparisons of the timepoint estimates at Days 28 and 60, if warranted. The proportional hazards assumption necessary for both the log rank test and Cox's proportional hazards model will be assessed. Any alternative methods used will be described in the CSR.

Two sensitivity analyses will be conducted mirroring analysis methods described above:

1. Excluding any imputed scores.
2. Imputing missing data when there is no collected data, as follows:
 - a. If there are missing scores prior to first occurrence of a \geq 2-point increase in the NIAID ordinal scale, then it will be assumed for purposes of this sensitivity analysis that the patient's score would have been equal to whatever score was recorded directly after the missing score

9.2.3. Change from baseline in overall symptom score, and individual symptom scores, as measured by the symptom score questionnaire up to Day 28

Change from baseline in the overall symptom score, and individual symptom scores from baseline to Day 28 will be analyzed using a mixed model repeated measures analysis using a missing at random assumption for handling missing data. The model will contain baseline symptom score, treatment arm, day, and treatment-by-day interaction as fixed effects, along with strata for the two randomization factors, as appropriate. The primary estimand of treatment effect

will be the treatment differences and corresponding 95% CIs, with p-values. Estimates and corresponding 95% CIs at days 7 and 14 will also be generated. Numbers and percentages of patients with each score at baseline, and days 7, 14, and 28 will also be summarized for the overall score and for each symptom by treatment arm. All available data will be used in the analysis; no imputation will be done for missing data.

The overall symptom score will be calculated as a sum of individual scores from 14 questions on the questionnaire. Each response will be scored according to the FDA's Guidance on "Assessing COVID-19-Related Symptoms in Outpatient Adult and Adolescent Subjects in Clinical Trials of Drugs and Biological Products for COVID-19 Prevention or Treatment" (US FDA, 2020). The scores correspond to the responses:

Questions 1-10: None = 0, Mild = 1, Moderate = 2, Severe = 3;

Questions 11-12: Not at all = 0, 1-2 times = 1, 3-4 times = 2, 5 or more times = 3;

Questions 13-14: Same as usual = 0, Less than usual = 1, No sense = 2.

A sensitivity analysis will be conducted mirroring the analysis methods described above but using the following assumptions:

- Completely exclude from analysis any patients who are missing more than 20% of their required symptom score questionnaires, unless the days where they are missing questionnaires fall after the patient experienced hospitalization, ER visit, or death.
- In patients with missing scores that account for 20% or less of their required symptom score questionnaires (or patients whose scores are missing due to prior hospitalization, ER visit, or death), handle as follows:
 - For any individual symptom scores that are missing because of the patient's prior death, impute the most severe possible answer.
 - If a patient has missing symptom scores during a period of hospitalization or ER visit, also impute the most severe possible answer for individual symptom scores.
 - For patients missing scores for any other reason, the higher of the two surrounding scores will be imputed for the missing individual symptom score (or scores).
 - The overall score will be calculated as the sum of individual symptom scores (reported or imputed) if possible.

Means and 95% CIs for the overall symptom score will be plotted over time from baseline through Day 28 by treatment arm (e.g., linear plot over time). Individual symptom scores will be summarized graphically using stacked bar charts at baseline and days 7, 14, and 28.

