6. ANALYSIS POPULATIONS/SETS

The following analysis populations will be used when performing statistical analyses or summaries:

- Screened Population includes all patients who are screened.
- Full Analysis Set (FAS) includes all randomized patients and will be analyzed according to treatment as randomized. This set is analogous to an Intent-to-Treat Population. This population will be used as the primary analysis population for baseline and efficacy analyses.
- Modified Intent-to-Treat (mITT) Population includes all randomized patients who meet eligibility criteria and receive at least one dose of any study treatment. Patients will be excluded from the mITT Population if they fail to meet eligibility criteria or if they do not receive any study treatment. This population will be used for sensitivity analyses and patients will be analyzed according to their randomized treatment.
- Safety Population/Set includes all randomized patients who receive at least one dose of any study treatment. Safety analyses will be performed according to the treatment received on Day 1.
- Biomarker Analysis Population includes all randomized patients who consent to provide additional samples for biomarker assessment and who receive at least one dose of any study treatment. Biomarker analyses will be performed according to the treatment received on Day 1.

A summary of the planned study analysis by patient population is displayed in [Table 1](#).

Table 1. Summary of Planned Analyses, by Population

Analysis	Screened	FAS	mITT	Safety	Biomarker
Participant Disposition	✓	✓			
Demographics and Baseline		✓	✓	✓	✓
Prior and Concomitant Medications, Procedures, and Surgeries		✓			
Medical History		✓			
Intercurrent Events		✓			
Primary Outcome Measure (Efficacy)		✓	✓ (sensitivity)		
Secondary Outcome Measures (Efficacy)		✓	If warranted (see Section 12.2)		
Other Efficacy Data (see Section 9.3)		✓			
Secondary Outcome Measures (Safety)				✓	
Exploratory Outcome Measures (Efficacy, non-biomarker)		✓			
Exploratory Outcome Measures (Safety, non-biomarker)				✓	
Exploratory Outcome Measures (Biomarker, Biomarker cohort only)					✓

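### The main NIAID progression analyses depend on a 5% missing-assessment trigger, above which an undefined high score may be imputed and create progression events

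*SAP*

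**What the plan says.** SAP Section 9.2 handles missing NIAID ordinal scores in steps.

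1. The medical monitor, blinded, imputes from hospitalization, oxygen, death and patient-reported records where possible.
2. A gap between two recorded scores takes the higher of the two.
3. For the rest, "any missing scores that are unable to be imputed will be ignored".
4. If these residual scores are under 5% of expected assessments, the impact is treated as negligible. At 5% or more, "the study team will consider imputing an appropriate" high score that is reasonable given the other responses, chosen and documented before unblinding.

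The same paragraph carries imputed scores into the analyses that follow, except where a sensitivity analysis says otherwise. Those analyses are:

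- **9.2.1:** the proportion with any increase of at least 2 points by Day 28 and Day 60, by Firth logistic regression. One committed sensitivity analysis excludes imputed scores, and a repeated measures model is optional.
- **9.2.2:** time to that event, with patients who have not progressed censored at their last non-missing assessment. It yields "Estimates for probability of progression at Days 7, 14, 28, and 60 days" from Kaplan-Meier, plus a Cox model. One of its two sensitivity analyses also excludes imputed scores.

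On population, "Secondary efficacy analyses will be performed using the FAS unless otherwise specified", and the "Full Analysis Set (FAS) includes all randomized patients". Section 9.2.1 does not say how a patient who leaves before Day 28 or Day 60 without observed progression is counted.

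**The concern.** Gaps between visits are already filled, so the residual missing scores lie mainly after a patient's last assessment. For an endpoint defined by any 2-point rise, one imputed score at or above that level settles the patient's outcome. The two sides of the trigger can therefore treat the same patient very differently. Below 5%, the later scores contribute nothing. At or above 5%, they may produce an event that nobody observed.

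A single imputed value of this kind does not estimate the progression rate. If it is applied equally in both arms, it raises both rates and dilutes the contrast. If missingness differs by arm, it shifts the risk difference towards or away from zero. Progression is likely to be uncommon, so a few per cent of imputed events could rival the observed ones. This is the first-listed secondary efficacy endpoint, and the rule also reaches the second.

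**Working it through.** **Inputs.** From SAP Section 4.1: "A total of approximately 500 patients will be randomized using a 1:1 assignment ratio", so 250 per arm; two-sided 0.05; and primary-endpoint rates "expected to be 2.4% for sargramostim and 8.0% for placebo". The SAP gives no NIAID progression rate and no expected amount of residual missing data. Both are assumptions here: progression at the primary-endpoint rates, and a fraction m of patients per arm affected.

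**Reproducing the plan's power.** With n per arm and p̄ the mean of the two rates, the pooled two-proportion formula is

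z = [|p₁ − p₀| − 1.96·√(2p̄(1−p̄)/n)] / √{[p₁(1−p₁) + p₀(1−p₀)]/n}.

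For 0.024 and 0.080: (0.0560 − 1.96 × 0.01986) / 0.01970 = 0.867, so power is 80.7%. This agrees with the stated figure of at least 80%.

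**All affected patients set to progressed.** The rate becomes p′ = p + m(1 − p). At m = 5%:

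- sargramostim: 0.024 + 0.05 × 0.976 = 0.0728
- placebo: 0.080 + 0.05 × 0.920 = 0.1260
- net added events: 250 × 0.05 × (0.976 + 0.920) = 23.7, on top of 250 × (0.024 + 0.080) = 26
- z = (0.0532 − 1.96 × 0.02676) / 0.02666 = 0.028, so power is 51.1%

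**Alternatives, same formula.** *Ignored* means affected patients count as not progressed, with rates p(1 − m). *Removed* means n(1 − m) patients at the original rates, a rough stand-in for censoring.

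| m | Ignored: rates | Ignored: power | Removed: power | Set to progressed: rates | Set to progressed: power |
|---|---|---|---|---|---|
| 5% | 2.3% vs 7.6% | 78.5% | 78.7% | 7.3% vs 12.6% | 51.1% |
| 10% | 2.2% vs 7.2% | 76.2% | 76.5% | 12.2% vs 17.2% | 35.6% |

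Ignoring the scores costs almost nothing in power relative to removing the patients. The loss comes from the high score.

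**One illustrative dataset.** Take 6/250 vs 20/250 observed progressors, with Firth logistic regression in the 2×2 case (0.5 added to each cell). With missing patients counted as not progressed, the risk difference is −5.6 points (95% CI −9.5 to −1.7), p = 0.009. Setting 25 patients (5% of 500) to progressed gives:

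| Split, sargramostim vs placebo | Risk difference, points | p |
|---|---|---|
| 12 vs 13 | −6.0 | 0.030 |
| 13 vs 12 | −5.2 | 0.059 |
| 15 vs 10 | −3.6 | 0.19 |
| 20 vs 5 | +0.4 | 0.88 |
| 5 vs 20 | −11.6 | 0.0001 |

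**Unit of the trigger.** The 5% counts assessments, and m counts patients. If four post-baseline assessments per patient were expected (an assumption), there would be 2,000 in all and the trigger would be 100. That could be 25 patients missing all four (5% of 500) or 100 patients missing one each (20%). Missing scores after Day 28 count toward the trigger but cannot affect the Day 28 endpoint.

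**The case against.** Much of the case against stands.

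- A reader might infer that crossing 5% switches the endpoint automatically from best-case to worst-case imputation. The text does not say so. The team only considers the option, the score must be reasonable given other responses, and it may fall short of a 2-point rise.
- A reader might infer that dropouts below the trigger are counted as non-progressors. That follows naturally from analysing all randomized patients, but 9.2.1 never states it. Excluding them is also possible, and in the example with 13 vs 12 missing it gives −5.9 points, p = 0.009.
- Record-based imputation comes first, so only a residue is exposed.
- The choice precedes unblinding, so it cannot be made on results by arm. The risk is bias and dilution.
- The difference from the primary endpoint, where patients lost to follow-up count as no event, is not a contradiction. These are different endpoints with different data.

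The strongest point is the committed 9.2.1 sensitivity analysis without imputed scores, which would make a large effect visible. It is only a partial safeguard. It also discards scores imputed from hospital, oxygen and death records, so a difference between the two analyses could not be attributed to the high score.

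It is also tempting to say that 9.2.2 already handles these patients properly by censoring. As written it does not, because imputed scores enter that analysis too and a high score at or above the 2-point rise would be an event there.

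**Conclusion.** The concern holds in a limited form. Section 9.2 leaves the main analyses of NIAID progression (9.2.1 and 9.2.2) subject to a threshold-triggered, discretionary single imputation whose value is not defined. That imputation can create progression events in patients with none observed.

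The fall in power from 81% to 51% is an outer bound and not a forecast. It rests on progression rates borrowed from the primary endpoint, on 5% of patients per arm being affected, and on every imputed score reaching the 2-point rise. A lower score or an unused option would reduce or remove the effect. A larger share of affected patients, which a trigger based on assessments allows, would increase it. The rule for ignoring residual scores is not itself a material power problem; its defect is that the patient's status in 9.2.1 is unstated. The plan should be changed, but the primary analysis is not affected.

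**What to change.** 1. Remove the high-score rule from the main analyses of 9.2.1 and 9.2.2. Keep it only as a sensitivity analysis labelled as a worst-case bound, with the score, patients and visits defined.
2. Use one prespecified method whatever the missing rate. One choice is the difference in Day 28 and Day 60 Kaplan-Meier progression probabilities, censoring at the last assessment and with no high-score imputation. The other is multiple imputation, as Section 9.1 already plans for the primary endpoint when 5% or more is missing.
3. State in 9.2.1 how patients without complete follow-up and without observed progression are counted.

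Moving to Kaplan-Meier estimates without the first change would not solve the problem.

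The cost is mainly SAP wording, since the Kaplan-Meier probabilities are already planned in 9.2.2. Multiple imputation would need some added programming. The price is reliance on non-informative censoring or on data missing at random, which the labelled bound would test.
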